# 26) Graded Laboratory Abnormalities Summary

The following labels will be used for treatment-emergent laboratory abnormalities and treatment-emergent Grade 3 or 4 laboratory abnormalities summary tables and listings:

Battery	Lab Test Label Used in l-labtox Listing	Toxicity Direction	Lab Test Label Used in t-labtox Table
	Hemoglobin	Decrease	Hemoglobin (Decreased)
	Lymphocytes	Decrease	Lymphocytes (Decreased)
Hematology	Neutrophils	Decrease	Neutrophils (Decreased)
	Platelets	Decrease	Platelets (Decreased)
	WBC	Decrease	WBC (Decreased)
	Albumin	Decrease	Albumin (Decreased)
	Alkaline Phosphatase	Increase	Alkaline Phosphatase (Increased)
	ALT	Increase	ALT (Increased)
	Amylase	Increase	Amylase (Increased)
	AST	Increase	AST (Increased)
	Bicarbonate	Decrease	Bicarbonate (Decreased)
	Corrected Calcium	Increase	Corrected Calcium (Hypercalcemia)
	Corrected Calcium	Decrease	Corrected Calcium (Hypocalcemia)
	Creatinine	Increase	Creatinine (Increased)
	GGT	Increase	GGT (Increased)
	Lipase	Increase	Lipase (Increased)
	Magnesium	Decrease	Magnesium (Hypomagnesemia)
	Phosphate	Decrease	Phosphate (Hypophosphatemia)
Chemistry	Serum Glucose (Fasting)	Increase	Serum Glucose (Fasting, Hyperglycemia)
Chemistry	Serum Glucose (Fasting)	Decrease	Serum Glucose (Fasting, Hypoglycemia)
	Serum Glucose (Nonfasting)	Increase	Serum Glucose (Nonfasting, Hyperglycemia)
	Serum Glucose (Nonfasting)	Decrease	Serum Glucose (Nonfasting, Hypoglycemia)
	Serum Potassium	Increase	Serum Potassium (Hyperkalemia)
	Serum Potassium	Decrease	Serum Potassium (Hypokalemia)
	Serum Sodium	Increase	Serum Sodium (Hypernatremia)
	Serum Sodium	Decrease	Serum Sodium (Hyponatremia)
	Total Bilirubin	Increase	Total Bilirubin (Hyperbilirubinemia)
	Total Cholesterol (Fasting)	Increase	Total Cholesterol (Fasting, Hypercholesterolemia)
	Triglycerides (Fasting)	Increase	Triglycerides (Fasting, Increased)
	LDL (Fasting)	Increase	LDL (Fasting, Increased)
	Urea Nitrogen (BUN)	Increase	Urea Nitrogen (Increased)
	Uric Acid	Increase	Uric Acid (Hyperuricemia)
	Uric Acid	Decrease	Uric Acid (Hypouricemia)

Battery	Lab Test Label Used in l-labtox Listing	Toxicity Direction	Lab Test Label Used in t-labtox Table	
	Urine Blood (Dipstick)	Increase	Urine RBC (Hematuria, Quantitative or Dipstick)*	
T.I	Urine Glucose	Increase	Urine Glucose (Glycosuria)	
Urinalysis	Urine Protein	Increase	Urine Protein (Proteinuria)	
	Urine RBC (Quantitative)	Increase	Urine RBC (Hematuria, Quantitative or Dipstick)*	

\* Due to the reflexive nature of the quantitative urine RBC test, results will be combined with the dipstick test of urine blood as described below. General rule is that urine RBC (Quantitative) should always be used first (if available), no matter it is collected at the same time of Urine Blood (Dipstick) or not. The combined Urine RBC (hematuria, Quantitative or Dipstick) toxicity grade will be used for "Maximum treatment emergent toxicity grade" summary.

Is Post-BL Urine RBC (Quant.) Result Available?	Is BL Urine RBC (Quant.) Result Available?	Is Post-BL Urine Blood (Dipstick) Result Available?	Is BL Urine Blood (Dipstick) Result Available?	How to Determine Treatment- Emergent Toxicity for "Urine RBC (Hematuria, Quantitative or Dipstick)"
Yes	Yes	-	-	Compare post-BL Urine RBC (Quant.) toxicity grade to BL Urine RBC (Quant.) toxicity grade. If post- BL toxicity is greater than BL toxicity, then treatment-emergent
Yes	No	-	-	Treatment-emergent. Use post-BL Urine RBC (Quant.) toxicity grade.
No	-	Yes	Yes	Compare post-BL Urine Blood (Dipstick) toxicity grade to BL Urine Blood (Dipstick) toxicity grade. If post-BL toxicity is greater than BL toxicity, then treatment-emergent
No	-	Yes	No	Treatment-emergent. Use post-BL Urine Blood (Dipstick) toxicity grade.
No	-	No	-	Do not count subject in the denominator for "Urine RBC (Hematuria, Quantitative or Dipstick)"

BL Baseline. Quant Quantitative. "" means any value can be present (or it can be missing), as it does not affect the classification

# 27) Toxicity Grades:

- a) For toxicity grade summaries, include all post-baseline graded results up to 30 days after the last dose of study drug, not just those used in by-visit summaries.
- b) For nonfasting glucose, fasting glucose, fasting total cholesterol, fasting triglycerides and fasting LDL grading, as specified in SAP Section 7.2.2.1, the treatment-emergent flag cannot be determined for approximately half of the subjects. As a result, these records will be excluded from the "Maximum Treatment-emergent Toxicity Grade" summary in the "Treatment-emergent Laboratory Abnormalities", Treatment-emergent Grade 2, 3 or 4 Laboratory Abnormalities" or "Treatment-emergent Grade 3 or 4 Laboratory Abnormalities" summary tables. In addition, fasting glucose and nonfasting glucose will be listed as two separate laboratory tests in the "Graded Laboratory Abnormalities" and "Grade 3 or 4 Laboratory Abnormalities" listings. Only a maximum postbaseline toxicity flag will be displayed and the treatment-emergent flag will not be displayed for these tests when the treatment-emergent flag cannot be determined.
- c) Toxicity grades for CD4 will not be displayed in listings. CD4 is scheduled for collection following HIV infection and toxicity grades apply to HIV uninfected subjects.
- 28) Clarification for "Pharmacokinetic Blood Sampling Time Record" listing
  - a) A new variable "Sample age" will be added in this listing, defined as the duration in day between sample collection date and assay date, ie, sample age assay date sample collection date + 1.
  - b) SAMTIME (hours) sample collection time (xx:xx) last dose time before sample collection (xx:xx).
- 28) PK parameters at the individual subject level should be displayed with the following reported number of decimal places:
  - PK concentration data will be reported with 1 decimal place.
- 29) Concomitant nonstudy-drug ARV medications (ie, ARV medications other than study drug that are taken while receiving study drug) will be flagged in "Nonstudy-Drug Antiviral Medication" listing. The logic to define concomitant nonstudy-drug ARV is similar to concomitant non-ARV Medications (see details in Section 7.6.5)

## 30) Lipid modifying medication analyses:

- a) Lipid modifying medication is defined to be the concomitant medication with ATC2 CMCLAS term "LIPID MODIFYING AGENTS" and CMDECOD contains wording of "STATIN" in the ADCM dataset.
- b) Subjects who took lipid-modifying medications at study entry refer to the subjects who use of the lipid-modifying agents at study day 1 (ie, the first dose date). More specifically, subjects with "Lipid Modifying Agent Use at Study Entry" include those subjects in Safety Analysis Set with: 1) any selected CM record with the start date ≤ the first dose date, and 2) the end date of the selected CM record is ongoing or the end date of the selected CM record > the first dose date.
- c) Subjects who initiated lipid-modifying medications during the study include the subjects in the Safety Analysis Set who didn't take lipid-modifying medications at study entry and met the following criteria: 1) for subjects who permanently discontinued study drug with any selected CM record started after the first dose date and on and prior to the last dose date; 2) for subjects who are still on study drug with any selected CM records started after the first dose date.
- d) For lipid-modifying medications with the start date completely unknown, we assume the start date is on or before the first dose date, lipid-modifying medication was considered as being taken at study entry if the end date is not prior to the first dose date (ie, the end date is on or after the first dose date, completely unknown, or ongoing).
- e) Lipid modifying medications with the start date prior to the first dose date and the end date completely unknown were considered as being taken at study entry.
- 31) For figures, if at a visit where n (sample size) for any treatment group ≤ 5, data for that treatment group will not be displayed at the visit in figure (except the Kaplan-Meier figure), but all data will be included in the corresponding table summary.

#### 32) Baseline HBV and HCV infection:

• The following table presents the HBV and HCV tests with all possible values. Values that have an asterisk after them denote a "positive" (or "quantifiable" for HBV DNA and HCV RNA) result while all others denote a "negative" result.

Label	LBTESTCD	LBTEST	Possible Values
HBsAg	CNT63	Hep B Surface Ag	"Positive"*, "Positive, Confirmed"*, "Negative"
HBsAb	CNT353	anti-Hep B Surface Ag2 Qual	"Positive"*, "Negative"
HBcAb	CNT68	CNT68 Hepatitis B Core Total "Positive"*, "Negative"	
HBV DNA	GET1883	HBV DNA CAP/CTM 2.0-EDTA-CL	"No HBV DNA detected", "<20 IU/mL HBV DNA detected", ">170000000"*, NUMERICAL VALUE*
HCVAb	CNT350	Hepatitis C Virus Antibody	"Positive"*, "Indeterminate", "Negative"
HCV RNA	GET1881	HCV RNA CAP/CTM 2.0EDTA-CL	"No HCV RNA detected", "<15 IU/mL HCV RNA detected", NUMERICAL VALUE*

- For baseline infection, when considering the different laboratory tests, take the latest, non-missing record on or prior to the first dose date for each test (ie, HBsAg, HBsAb, HBcAb, and HBV DNA)
- a) The baseline infection status will be one of the three values: Yes/No/Null
- b) The following tables provide combinations of HBV and HCV tests and the corresponding baseline infection status

HBsAg	HBsAb	HBcAb	HBV DNA	Infection Status
Positive	-	-	-	Y
	Positive	-	-	N
			Quantifiable	Y
		Positive	Not Quantifiable	N
			Missing	Null
	Negative	Negative	-	N
			Quantifiable	Null
		Missing	Not Quantifiable	N
Negative			Missing	Null
		Positive	Quantifiable	Null
			Not Quantifiable	N
			Missing	Null
	Missing	Negative	-	N
		Missing	Quantifiable	Null
			Not Quantifiable	N
			Missing	Null
	Positive	-	-	Null
			Quantifiable	Y
		Positive	Not Quantifiable	Null
Missing	Negative		Missing	Null
		Negative	-	Null
		Missing	-	Null
	Missing	-	-	Null

HCVAb	HCV RNA	Infection Status
Positive	Quantifiable	Y
	Not Quantifiable	N
	Missing	Null
Negative	-	N
Missing	Quantifiable	Null
	Not Quantifiable	N
	Missing	Null

"" means any value can be present, as it does not affect the classification

- 33) For race, any black includes black and mixed races with any black ancestry (mixed black). Mixed black include Race "Other" when the Other Specify term includes 'BLACK' or 'AFR'. Race subgroup analyses (ie, black vs. nonblack) will exclude subjects with Race "Not Permitted."
- 34) CASI questionnaire dynamic questions
  - a) Screening CASI: Men Bottom [or Top] without condom last 90 days
    - If QSTEST 'Men Bottom [or Top] without condom last 90 days' is missing, but 'Men Bottom [or Top] last 90 days' 0 then summarize 'Men Bottom [or Top] without condom last 90 days' 0
  - b) Baseline CASI: Men Bottom [or Top] wo Condom since Screening
    - If QSTEST 'Men Bottom [or Top] wo Condom since Screening' is missing, but 'Men had Sex with since Screening' 0 then summarize 'Men Bottom [or Top] wo Condom since Screening' 0
  - c) Follow Up CASI:
    - If QSTEST 'Men Bottom [or Top] wo Condom since last visit' is missing, but 'Men had Sex with since last study visit' 0 then summarize 'Men Bottom [or Top] wo Condom since Screening' 0
    - If QSTEST 'Days Missed Tablets 7 Days BEFORE Sex [or AFTER Sex]' is missing, but 'Men Top without Condom since last visit' 0 and 'Men Bottom wo Condom since last visit' 0 then summarize 'Days Missed Tablets 7 Days BEFORE Sex [or AFTER Sex]' Not applicable
- 35) Identifying PEP versus PrEP from ARV medications:

Exclude any records that we are unable to classify as PEP or PrEP: (CMDECOD 'BLINDED INVESTIGATIONAL DRUG' or 'UNKNOWN DRUG') and CMTRT does not contain any of the following terms 'PREP' 'PRE EXPOSURE PROPHYLAXIS' 'PEP' 'POST EXPOSURE PROPHYLAXIS', 'CAB'

- a) PrEP:
  - i) either cabotegravir (CMDECOD 'NON-GILEAD INVESTIGATIONAL DRUG' or CMDECOD 'BLINDED INVESTIGATIONAL DRUG') and CMTRT contains 'CAB'
  - ii) F/TDF or generic F/TDF medication for PrEP is defined as any treatment course that includes both FTC and TDF without any other 3rd ARV agents as follows:
    - (1) F/TDF: CMDECOD 'TRUVADA' or
    - (2) Generic F/TDF: overlapping medications of CMDECOD 'EMTRICITABINE' and CMDECOD 'TENOFOVIR DF' where the medication start and end dates overlap or

(3) Potential F/TDF for PrEP: CMDECOD ("BLINDED INVESTIGATIONAL DRUG or 'UNKNOWN DRUG') and (CMTRT includes 'PREP' or 'PRE EXPOSURE PROPHYLAXIS')

and

(4) where there are no other overlapping ARV medications (excluding cabotegravir or HIV vaccine)

At any time that the medication start and end dates of F/TDF (or generic F/TDF) does not overlap with any other medication start and end dates of another ARV agent (or overlaps by 1 day), that F/TDF (or generic F/TDF) record will be considered as treatment for PrEP.

Each ARV agent can be matched to only 1 F/TDF (or generic F/TDF) record, however, a single F/TDF (or generic F/TDF) record may be considered as taken both for PEP and PrEP if the F/TDF record start and/or end date extends past the other ARV agent start and/or end date.

If a partial month/year (or year only) medication end date and consecutive medication start date exactly match, these records will not be considered overlapping.

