## 3.6. Missing Data and Outliers

# 3.6.1. Missing Data

A missing datum for a given study analysis window may be due to any of the following reasons:

- A visit occurring in the window but data were not collected or were unusable
- A visit not occurring in the window
- A subject prematurely discontinuing from the study before reaching the window

In general, missing data will not be imputed unless methods for handling missing data are specified. Exceptions are presented in this document.

For the secondary endpoints of the percent changes from baseline in hip BMD and spine BMD in a subset of subjects, urine beta-2-microglobulin to creatinine ratio, and urine RBP to creatinine ratio, the distribution of UP and UPCR categories and the change from baseline in serum creatinine, missing values will be imputed using the last observation carried forward (LOCF) method and baseline observation carried forward (BlOCF) method.

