# 3.8.2. Analysis Windows

Subject visits might not occur on protocol specified days. Therefore, for the purpose of analysis, observations collected from the DB phase of the study (ie, DB phase data) will be assigned to analysis window. Observations collected from the OLE phase of the study (ie, OLE phase data) will not have analysis window assigned and will be included in listings with derived visit marked as "Extension".

The CASI questionnaire assessment consists of different versions of the questionnaire corresponding to 3 different time periods: screening, baseline and follow-up. All versions of the CASI questionnaire include questions regarding number of sexual partners. For the CASI Screening questionnaire items regarding the number of sexual partners in the last 90 days, the analysis windows are defined as prior to the first dose date. For the CASI Baseline questionnaire items, the analysis windows are defined up to or on the first dose date.

Aside from the number of sexual partners, other items collected in the CASI Screening questionnaire are unique to the screening questionnaire and collected only once (including education, circumcision, drug use, management of HIV risk, etc.) All of these other CASI Screening questionnaire items will be summarized for the Screening visit without applying an analysis window.

The analysis windows for HIV, hematology, chemistry (including glucose), urinalysis, renal biomarkers, eGFRCG, vital signs, weight, CASI Follow-Up questionnaire, and DBS are presented in Table 3-1.

Table 3-1. Analysis Windows for HIV, Hematology, Chemistry, Urinalysis, Renal Biomarkers, eGFRCG, Vital Signs, Weight, CASI Follow-Up Questionnaire, and DBS

Visit ID	Nominal Day	Lower Limit	Upper Limit
Baseline	1	(none)	1
Week 4	28	2	56
Week 12	84	57	126
Week 24	168	127	210
Week 36	252	211	294
Week 48	336	295	378
Week 60	420	379	462
Week 72	504	463	546
Week 84	588	547	630
Week 96	672	631	714
Week 108	756	715	798
Week 120	840	799	882
Week K (K is every 12 weeks after previous visit)	K*7	(K-6)*7+1	(K+6)*7

HIV laboratory tests include both Covance central laboratory tests (HIV antibody screening tests, HIV Antibody Supplemental tests, qualitative and quantitative tests) and local laboratory tests (rapid HIV 1 Ag/Ab test or other local laboratory tests collected from eCRFs).

CASI follow up questionnaire collected at post baseline visits only, no baseline analysis window will be applied.

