# 9.3. Anal Intercourse Partners While At Risk of HIV Infection During the DB phase (CASI Questionnaire)

The number of anal intercourse partners from CASI questionnaire responses will be summarized by treatment group and visit while at risk of HIV infection during the study, using descriptive statistics (n, mean, SD, median, Q1, Q3, minimum, and maximum) as well as the number and percentage of subjects with 0, 1, 2, 3, 4-5, 6-10 and  $\geq$  11 partners on the FAS. The following summaries of number of anal intercourse partners will be provided:

- Unprotected Receptive Anal Intercourse (URAI) Partners
- Unprotected Insertive Anal Intercourse (UIAI) Partners
- Anal Intercourse Partners

While at risk of HIV infection during the study includes visits occurring through the upper limit of the analysis window corresponding to the last at-risk of HIV infection date as defined in Section 6.2.3.

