- 12) Please note, "Not Permitted", "Unknown", "Not Applicable", "Not Done" or missing categories will be excluded for percentage calculation and also excluded for p-value generation for categorical data analysis (ie, CMH test or Fisher exact test). For the number of subjects with each syphilis stage and syphilis status summarized among subjects with a syphilis diagnosis, no p-values will be generated.
- 13) SAS code for the treatment comparison for duration of exposure. The p-value from log rank test should be used.

```
proc lifetest data=ADSL method=km;
   time TRTDURD*ESDD(0); /*Derive ESDD from COMT01FL, where ESDD = 0
   indicates censored observation (ie, subject is still on study drug)*/
   Strata TRT01AN;
   label TRTDURD = "Duration of Exposure (Days)";
run;
```

- 14) Last Dose Date and Last Study Date
  - a) Last Dose Date (ie, TRTEDTC, TRTEDT, TR01EDT or TR01EDTC) in ADSL was defined in Section 3.8.1 for subjects who prematurely discontinued or completed study drug in the 'blinded treatment' study phase.

If study drug start date or end date are partially missing (ie, only year and month are known), the day will be imputed as 15 for the purpose of this analysis.

For subjects with a partial last dosing date (ie, month and year of last dose are known), use the max (the dispensing dates of study drug bottles, study drug start dates and end dates, imputed end date of last dose [day imputed as 15]) as the final imputed last dose date. (However, if dispensing date's month is after last dose date's month, data query is needed.)

For subjects where only the year of the last dosing date is known), then impute the last dose date based on the below:

Condition	Last dose date (year only) is imputed as
The year of the last dose is equal to the year of the last visit*	Maximum of study drug start dates and end dates, clinic visit dates and laboratory visit dates excluding the 30-day follow-up visit
The year of the last dose is before the year of the last visit*	December 31st of the last dose year
The year of the last dose is after the year of the last visit*	Data query is needed. If this remains unchanged after query, impute as:  January 1 st of the last dose year

\*Last visit is defined as the maximum of clinic visit dates and laboratory visit dates excluding the 30 day follow up visit.

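### SAP Appendix 12 item 34(c) sets the wrong CASI item to zero at follow-up; programmed literally, no-partner records would leave the by-visit URAI/UIAI tables

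*SAP*

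**What the plan says.** SAP Appendix 12 item 34 covers CASI questions that may be blank because an earlier answer made them irrelevant. It has one rule per questionnaire version. (A bare 0 in the quotes reads as equal to 0.)

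- Screening, 34(a): "Men Bottom [or Top] last 90 days' 0 then summarize 'Men Bottom [or Top] without condom last 90 days' 0".
- Baseline, 34(b): "Men had Sex with since Screening' 0 then summarize 'Men Bottom [or Top] wo Condom since Screening' 0".
- Follow-up, 34(c). The condition is "If QSTEST 'Men Bottom [or Top] wo Condom since last visit' is missing, but 'Men had Sex with since last study visit' 0 then", and the action is given in "Men had Sex with since last study visit' 0 then summarize 'Men Bottom [or Top] wo Condom since Screening' 0".

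A second bullet in 34(c) codes the questions on tablets missed before and after sex as not applicable, provided that both since-last-visit condomless items (top and bottom) equal 0.

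The follow-up items feed SAP Section 9.3, which summarises partner counts by visit and treatment group in the FAS. The rows include "Unprotected Receptive Anal Intercourse (URAI) Partners" and the matching insertive row (UIAI), each with means, medians and a category for 0 partners.

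**The concern.** The follow-up rule tests one item and fills another. The item it fills belongs to the baseline questionnaire, and its wording matches the target of 34(b). If a programmer executes the rule as written, the follow-up item stays missing for exactly the people the rule is meant to count as zero.

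The level of condomless exposure shown during follow-up is then at stake. Participants with no partners would be kept as zeros at screening and baseline, but would drop out of the URAI and UIAI rows afterwards. The remaining mean would be too high and the 0 category too small.

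**Working it through.** The documents state no figure on this point, so there is none to reproduce. The check has two parts: what happens to a blank follow-up item, and how much that could change the table.

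**Item tested against item filled**

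| Rule | Item tested for missing | Item set to 0 | Same item? |
|---|---|---|---|
| 34(a) screening | condomless partners, last 90 days | condomless partners, last 90 days | yes |
| 34(b) baseline | condomless partners since Screening | condomless partners since Screening | yes |
| 34(c) follow-up | condomless partners since last visit | condomless partners since Screening | no |

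**Whether another rule fills the follow-up item**

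1. The versions are separate instruments. SAP Section 3.8.2 states: "The CASI questionnaire assessment consists of different versions of the questionnaire corresponding to 3 different time periods: screening, baseline and follow-up". It limits the baseline items to dates up to and including the first dose, so a zero written to the baseline item from a later record falls outside that item's window.
2. The default is no imputation. SAP Section 3.6.1 states: "In general, missing data will not be imputed unless methods for handling missing data are specified". No other rule assigns the follow-up zero.
3. Blank values do not enter the category percentages. Appendix 12 item 12 says that "missing categories will be excluded for percentage calculation".

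So, read literally, the record stays missing and leaves the URAI and UIAI rows for that visit. The not-applicable bullet cannot apply to it either, because its condition needs both since-last-visit items to equal 0.

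**Size**

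Let s be the share of responders at a visit with no partners and a skipped condomless item, and let m be the mean condomless-partner count among the rest.

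- Corrected rule: mean = (1 − s) × m + s × 0 = (1 − s) × m.
- Literal rule: mean = m.
- Ratio of literal to corrected: 1/(1 − s).

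For the 0 category, let q be the share of the rest with 0 condomless partners. The literal rule shows q; the corrected rule shows s + (1 − s) × q. The documents give neither s nor q. The table assumes a range for s and q = 30%.

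| s (assumed) | Mean too high by | 0 category, literal | 0 category, corrected |
|---|---|---|---|
| 2% | 1/0.98 − 1 = 2.0% | 30% | 31.4% |
| 5% | 1/0.95 − 1 = 5.3% | 30% | 33.5% |
| 10% | 1/0.90 − 1 = 11.1% | 30% | 37.0% |
| 20% | 1/0.80 − 1 = 25.0% | 30% | 44.0% |
| 30% | 1/0.70 − 1 = 42.9% | 30% | 51.0% |

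**The case against.** The strongest reply is that the intent is plain. The bullet sits under the follow-up questionnaire, its condition uses follow-up items only, its two sister rules fill what they test, and the next bullet relies on the since-last-visit items being 0. Writing to a baseline item from a follow-up record serves no stated purpose. A programmer who follows the evident intent produces correct tables. This stands: the loss of records is conditional on literal programming. It does not remove the need for a correction, because a programming specification is there to be executed as written.

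The rule also acts only where the condomless item is blank. The documents do not show the CASI skip logic, so a reader should not infer that every follow-up visit without sex would be lost.

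The Section 9.3 table could reveal the error. It also has a row for all anal intercourse partners, which item 34 does not address. A lower n in the URAI and UIAI rows than in that row would be a visible sign.

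Finally, the output carries little weight. Section 9.3 is descriptive and names no test. The efficacy subgroup on URAI partners (SAP Section 3.4.1) uses screening answers, and the predicted HIV incidence in SAP Appendix 8 uses rectal gonorrhea rates rather than CASI. This stands too, and it sets the severity.

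**Conclusion.** The follow-up rule is wrong as written, and the severity is minor. If it is programmed literally, and if the condomless item is skipped by people with no partners, those records leave the by-visit URAI and UIAI summaries. The mean among responders is then too high by 1/(1 − s), or +2% to +43% for assumed s of 2% to 30%. The not-applicable coding for missed tablets also fails for them. HIV incidence, the non-inferiority test and the efficacy subgroups are untouched.

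Three stronger readings are tempting, but the documents do not support them:

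- That risk would appear to rise after baseline. Section 9.3 plans no change-from-baseline analysis. The partner counts in SAP Section 5.3 use a 90-day recall at screening in the Safety Analysis Set, while Section 9.3 uses visit intervals in the FAS, so the levels are not directly comparable in any case.
- That the distortion is largest at Week 4. SAP Section 4.2.3.2 does give a 28-day interval there, and a shorter recall could plausibly raise s, but no value of s by visit is given.
- That the comparison between arms is biased. The rule is the same in both arms, so this would need s to differ by arm, and nothing in the documents suggests that it does.

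**What to change.** In SAP Appendix 12 item 34(c), change the target of the first bullet to the item it tests: *Men Bottom [or Top] wo Condom since last visit* = 0. Leave 34(a), 34(b) and the second bullet of 34(c) as they are; the second bullet then works as intended.

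Confirm that the existing code and any delivered Section 9.3 tables used that target. As a quick screen, compare n by visit in the URAI and UIAI rows with n in the row for all anal intercourse partners. A shortfall calls for a look at the code, although ordinary item non-response could also cause one.

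The cost is one phrase in the programming specification and a short code check, with a rerun of the descriptive tables only if the literal target was used. I see no downside.
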